Revised Protocol 1 (Final Approved 2.0)	02 March 2018	
1. Incorporates changes to multiple Sections of the protocol in response to additional internal review:2. Revises secondary and exploratory objectives and endpoints3. Revises the protocol to more clearly define expectations for participants who discontinue study medication or overall study participation4. Clarifies visit intervals and visit windows for bone mineral density and immunogenicity follow-up visits5. Clarifies pregnancy reporting requirements6. Clarifies procedures for collection of serious adverse events and concomitant medications7. Updated methods of data analysis8. Provides clarifications to increase consistency within the protocol.	[REDACTED]
Revised Protocol 2 (Final Approved 3.0)	20 January 2019	
1. Updates the Sponsor's contact information and includes the study name (FALCON 2) and generic name, pgebelfermin, for BMS-9860362. Updates the screening/rescreening processes and sequence/timing of required testing, e.g., allows	[REDACTED]

		
extension of screening period (from 8 to 12 weeks) if needed
 
3. Modifies the inclusion criteria of patients with hepatitis C virus sustained viral response (for at least 2 years)
 
4. Updates inclusion/exclusion criteria for medications
 
5. Allows inclusion of participants with Grade \leq 1 varices (from historical esophagogastroduodenoscopy) and updates inclusion/exclusion criteria for Fibroscan elastography and medications
 
6. [REDACTED]
 
7. Provides for the collection of medications that could impact bone mineral density from end of treatment through the 6-month follow-up dual-energy X-ray absorptiometry scan
 
8. Updates requirements for procedures and testing for subjects prematurely discontinuing study treatment
 
9. Updates and clarifies study procedures and analysis plans
 
10. Incorporates editorial updates
	
Revised Protocol 3 (Final Approved 4.0)	30 January 2020	
1. Updates made throughout the protocol requiring all participants to have sample collection for potential immunogenicity testing during the visit at 6 months after the Week 52 Post-treatment Follow-up (PTFU) Visit.
 
2. Updated Section 1 Schedule of Activities, Table 1 and Table 2, Clinical Efficacy Assessments, Hepatic Magnetic Resonance Elastography (MRE), participants to fast at least 4 hours prior to assessment to align with instructions in the imaging manual.
	[REDACTED] [REDACTED]

		
3. Updates the number of randomized participants from approximately 100 to approximately 155 (approximately 38 participants per arm) based on final enrollment. See Section 6.2 for details.4. Update to Section 1 and Section 8.4.8 to include collection of any other nonalcoholic steatohepatitis (NASH) therapies taken during the post Week 52 follow-up period during the visit at 6 months after the Week 52 PTFU Visit.5. Updates made throughout the protocol to clarify the exploratory endpoint related to digital pathology assessment of liver biopsies.6. Update to Section 8.5.1.1 to include handling of incidental findings and blinding of on-treatment biopsy results.7. Update to Section 9.4.4 to remove endpoints that reference relationships to align with the Statistical Analysis Plan (SAP).	
--	--	---	--

1. SCHEDULE OF ACTIVITIES

Schedules of procedures and assessments are described in the tables below:

- [Table 1](#) - Screening Period Activities - Study MB130-069
- [Table 2](#) - Double-Blind Treatment Period Activities and Post-Treatment Follow-Up Period Activities - Study MB130-069
- [Table 3](#) - Long-Term Bone Mineral Density and Immunogenicity Follow-Up Period Activities - Study MB130-069

Table 1 Screening Period Activities - Study MB130-069

Procedure/Assessment	Screening Period (up to 8 weeks; see Section 8.1)	Notes
Screening and History Assessments		
Informed consent	X	The approved informed consent form must be signed before completing any protocol-specific procedures
Study enrollment via interactive response technology (IRT)	X	See Section 8.4.3
Inclusion/exclusion criteria	X	See Sections 8.3.1, 8.3.2, 8.3.3, and 8.3.4
Complete medical history	X	See Section 8.3.5, Appendix 4
Surgical history	X	See Section 8.3.5
Diet and exercise history	X	See Section 8.3.5
Prior medications	X	See Section 8.4.8
Dietary and Lifestyle Counseling	X	See Section 8.3.6
Clinical Efficacy Assessments		
Liver biopsy	X	Only to be conducted if no liver biopsy specimen collected within 6 months (26 weeks) prior to informed consent is available and readable by the Central Pathologist. See Section 8.5.1.1.
Hepatic magnetic resonance elastography (MRE)	X	See Section 8.5.1.3. Participants should fast for at least 4 hours prior to assessment
Hepatic magnetic resonance imaging (MRI)	X	See Section 8.5.1.3
Fibroscan® elastography	X	See Section 8.5.1.4
Height and weight for body mass index (BMI) calculation	X	See Section 8.5.1.6
Waist circumference	X	See Section 8.5.1.6
Child-Pugh Turcotte scoring	X	See Section 8.5.1.7, Appendix 5

Procedure/Assessment	Screening Period (up to 8 weeks; see Section 8.1)	Notes
		Screening Period may be extended to a total of up to 12 weeks upon discussion with the medical monitor
Model for End-Stage Liver Disease (MELD) scoring	X	See Section 8.5.1.8 and Appendix 10
Clinical Safety Assessments		
12-lead electrocardiogram	X	If a participant has a QT interval corrected using Fridericia's formula (QTcF) > 480 msec, it should be confirmed by repeat electrocardiogram 30-60 minutes after the initial electrocardiogram. If the QTcF is confirmed to be > 480 msec, the participant should not be allowed to participate in the study. See Section 8.5.3.5
Vital signs	X	See Section 8.5.3.4
Physical examination	X	Examination will be a full physical examination as described in Section 8.5.3.3
Dual-energy X-ray absorptiometry (DXA) assessment	X	See Section 8.5.3.8
Laboratory Assessments		
Urinalysis	X	Includes assessments listed in Table 8 in Section 8.5.4
Urine for inflammation and kidney markers	X	See Table 8 in Section 8.5.4
Urine drug screen	X	See Table 8 in Section 8.5.4
Serum pregnancy test	X	To be conducted only in women of childbearing potential. See Table 8 in Section 8.5.4
Follicle-stimulating hormone (FSH) testing	X	To be conducted only in postmenopausal women. See Table 8 in Section 8.5.4 and Appendix 2
Hepatitis B assessments	X	See Table 8 in Section 8.5.4 and Appendix 3
Hepatitis C assessments	X	See Table 8 in Section 8.5.4 and Appendix 3
Hematology	X	Includes the assessments listed in Table 8 in Section 8.5.4
Blood chemistry	X	Includes the assessments listed in Table 8 in Section 8.5.4

Procedure/Assessment	Screening Period (up to 8 weeks; see Section 8.1)	Notes
		Screening Period may be extended to a total of up to 12 weeks upon discussion with the medical monitor
Laboratory metabolic markers	X	See Section 8.5.1.6 and Table 8 in Section 8.5.4. Participants should fast for at least 8 hours prior to the blood collection for these assessments
Serum N-terminal type 3 collagen propeptide (PRO-C3)	X	See Table 8 in Section 8.5.4 Participants should fast for at least 8 hours prior to the blood collection for this assessment
Adiponectin	X	See Table 8 in Section 8.5.4. Participants should fast for at least 8 hours prior to the blood collection for this assessment
Micro RNA (miRNA)	X	See Table 8 in Section 8.5.4
Whole blood for gene expression assessments	X	See Table 8 in Section 8.5.4

Table 2 Double-Blind Treatment Period Activities and Post-Treatment Follow-Up Period Activities - Study MB130-069

Procedure/Assessment	Double-Blind Treatment					Follow-Up	
	Day 1 Visit	After Day 1, up to Week 24 Visits every 4 weeks (± 5 days)	Week 24 Visit (± 5 days)	After Week 24, up to Week 48 Visits every 8 weeks (± 5 days)	Week 48 Visit (± 5 days)/ Early Termination (ET)		
Screening and History Assessment Updates							
Inclusion/exclusion criteria	X						Confirm continued study eligibility. See Sections 8.3.1 , 8.3.2 , 8.3.3 , and 8.3.4
Confirm continued eligibility and randomization via interactive response technology (IRT)	X						See Section 8.4.3
Update medical history	X						See Section 8.3.5
Update surgical history	X						See Section 8.3.5
Diet and exercise history	X		X		X		See Section 8.3.5
Prior medications	X						See Section 8.4.8

Procedure/Assessment	Double-Blind Treatment					Follow-Up	
	Day 1 Visit	After Day 1, up to Week 24 Visits every 4 weeks (± 5 days)	Week 24 Visit (± 5 days)	After Week 24, up to Week 48 Visits every 8 weeks (± 5 days)	Week 48 Visit (± 5 days)/ Early Termination (ET)		
Clinical Efficacy Assessments							
Liver biopsy					X		
See Section 8.5.1.1
 
The biopsy should be performed within ± 7 days of the Week 48 Visit. However, if a biopsy cannot be scheduled within the window specified above, the biopsy should be performed as close to schedule as possible
 
Liver biopsy will be performed at the ET Visit if the participant has completed at least Week 20. If a participant discontinues study participation prior to Week 20 they should consider having a liver biopsy at ET

Hepatic magnetic resonance elastography (MRE)			X		X		
Assessment window ± 7 days. See Section 8.5.1.3. Participants should fast for at least 4 hours prior to these assessments. For participants prematurely discontinuing study medication prior to Week 24, MRE should be conducted at the ET Visit if the date of discontinuation is more than 4 weeks from the date of the previous MRE. For participants prematurely discontinuing study medication after Week 24, MRE should be conducted at the ET Visit if the date of

Procedure/Assessment	Double-Blind Treatment					Follow-Up	
	Day 1 Visit	After Day 1, up to Week 24 Visits every 4 weeks (± 5 days)	Week 24 Visit (± 5 days)	After Week 24, up to Week 48 Visits every 8 weeks (± 5 days)	Week 48 Visit (± 5 days)/ Early Termination (ET)		
							discontinuation is more than 8 weeks from the date of the previous MRE
Hepatic magnetic resonance imaging (MRI)			X		X		Assessment window \pm 7 days. See Section 8.5.1.3. For participants prematurely discontinuing study medication prior to Week 24, MRI should be conducted at the ET Visit if the date of discontinuation is more than 4 weeks from the date of the previous MRI. For participants prematurely discontinuing study medication after Week 24, MRI should be conducted at the ET Visit if the date of discontinuation is more than 8 weeks from the date of the previous MRI
Fibroscan® elastography					X		See Section 8.5.1.4

Procedure/Assessment	Double-Blind Treatment					Follow-Up	
	Day 1 Visit	After Day 1, up to Week 24 Visits every 4 weeks (± 5 days)	Week 24 Visit (± 5 days)	After Week 24, up to Week 48 Visits every 8 weeks (± 5 days)	Week 48 Visit (± 5 days)/ Early Termination (ET)		
Weight for body mass index (BMI) calculation	X		X		X	X	See Section 8.5.1.6. The Screening value for height will be used in the BMI calculation
Waist circumference	X		X		X		See Section 8.5.1.6
Child-Pugh Turcotte scoring	X		X		X		See Section 8.5.1.7, Appendix 5
Model for End-Stage Liver Disease (MELD) scoring	X	X	X	X	X	X	All components of the MELD score should be completed on the same day. If any individual component needs to be repeated on another day, all other components must be repeated as well. See Section 8.5.1.8 and Appendix 10
Liver-related clinical outcome events	X	X	X	X	X	X	See Section 8.5.1.9
3-Level EuroQol 5 Dimension (EQ-5D-3L) quality-of-life questionnaire	X		X		X		See Section 8.5.1.10
36-Question Short Form Health Survey (SF-36) Version 2	X		X		X		See Section 8.5.1.10
Chronic Liver Disease Questionnaire-Nonalcoholic Fatty Liver Disease (CLDQ-NAFLD)	X		X		X		See Section 8.5.1.10
Clinical Safety Assessments							
Adverse events	X	X	X	X	X	X	See Section 8.5.3.1 and Appendix 9
Concomitant medications	X	X	X	X	X	X	See Section 8.3.7

Procedure/Assessment	Double-Blind Treatment					Follow-Up	
	Day 1 Visit	After Day 1, up to Week 24 Visits every 4 weeks (± 5 days)	Week 24 Visit (± 5 days)	After Week 24, up to Week 48 Visits every 8 weeks (± 5 days)	Week 48 Visit (± 5 days)/ Early Termination (ET)		
12-lead electrocardiogram	X		X		X	X	If a participant has a QTcF>480 msec at an on-treatment visit, it should be confirmed by repeat ECG 30-60 minutes after the initial ECG. If the QTcF is confirmed to be >480 msec, the medical monitor should be contacted. See Section 8.5.3.5 and Table 9 in Section 8.5.5
Vital signs	X	X	X	X	X	X	See Section 8.5.3.4
Full physical examination			X		X	X	See Section 8.5.3.3
Abbreviated physical examination	X	X		X			See Section 8.5.3.3
Dual-energy X-ray absorptiometry (DXA)					X		See Section 8.5.3.8. Assessment window \pm 7 days Participants will return for a follow-up DXA assessment 6 months after the Week 52/PTFU Visit (see Table 3). One month is defined as 4 calendar weeks. The ET Visit should include a DXA scan only if the participant has completed at least the Week 16 Visit
Laboratory Assessments - On days of study visits, participants will hold their study medication dose until all laboratory samples have been collected.							
Urinalysis	X	X	X	X	X	X	See Section 8.5.4 and Table 8 in Section 8.5.4

Procedure/Assessment	Double-Blind Treatment					Follow-Up	
	Day 1 Visit	After Day 1, up to Week 24 Visits every 4 weeks (\pm 5 days)	Week 24 Visit (\pm 5 days)	After Week 24, up to Week 48 Visits every 8 weeks (\pm 5 days)	Week 48 Visit (\pm 5 days)/ Early Termination (ET)		
Serum or urine pregnancy test	X	X	X	X	X	X	To be conducted in women of childbearing potential only. See Table 8 in Section 8.5.4
Enhanced Liver Fibrosis (ELF) Assessment	X		X		X		See Section 8.5.4 and Table 8 in Section 8.5.4. Participants should fast for at least 8 hours prior to the blood collection for this assessment
Hematology	X	X	X	X	X	X	See Section 8.5.4 and Table 8 in Section 8.5.4
Blood chemistry	X	X	X	X	X	X	See Section 8.5.4 and Table 8 in Section 8.5.4
Anti-drug and anti-FGF21 antibodies	X	X	X	X	X	X	See Table 8 in Section 8.5.4. Any participant with anti-drug and/or anti-FGF21 antibodies at Week 52/PTFU or ET who has not demonstrated decreasing anti-drug and/or anti-FGF21 antibody titers will be followed for up to approximately 14 months after Week 52/PTFU as described in Section 8.5.3.6. One month is defined as 4 calendar weeks

Procedure/Assessment	Double-Blind Treatment					Follow-Up	
	Day 1 Visit	After Day 1, up to Week 24 Visits every 4 weeks (± 5 days)	Week 24 Visit (± 5 days)	After Week 24, up to Week 48 Visits every 8 weeks (± 5 days)	Week 48 Visit (± 5 days)/ Early Termination (ET)		
Laboratory metabolic markers	X		X		X		See Section 8.5.1, Section 8.5.4 and Table 8 in Section 8.5.4. Participants should fast for at least 8 hours prior to the blood collection for these assessments
Serum N-terminal type 3 collagen propeptide (PRO-C3)	X	X Samples only to be collected at Week 4, Week 8, and Week 12	X		X	X	See Section 8.5.1, Section 8.5.4, and Table 8 in Section 8.5.4. Participants should fast for at least 8 hours prior to the blood collection for this assessment

Procedure/Assessment	Double-Blind Treatment					Follow-Up	
	Day 1 Visit	After Day 1, up to Week 24 Visits every 4 weeks (± 5 days)	Week 24 Visit (± 5 days)	After Week 24, up to Week 48 Visits every 8 weeks (± 5 days)	Week 48 Visit (± 5 days)/ Early Termination (ET)		
Adiponectin	X	X Samples only to be collected at Week 4, Week 8, and Week 12	X		X	X	See Section 8.5.1 and Table 8 in Section 8.5.4 Participants should fast for at least 8 hours prior to the blood collection for this assessment
Micro RNA (miRNA)	X	X Samples only to be collected at Week 4, Week 8, and Week 12	X		X	X	See Section 8.5.4 and Table 8 in Section 8.5.4
Whole blood for gene expression assessments	X	X Samples only to be collected at Week 4, Week 8, and Week 12	X		X	X	See Section 8.5.4 and Table 8 in Section 8.5.4
Serum for disease, target and drug effect biomarkers	X	X Samples only to be collected at Week 4, Week 8, and Week 12	X		X	X	See Section 8.5.4 and Table 8 in Section 8.5.4. Participants should fast for at least 8 hours prior to the sample collection

Procedure/Assessment	Double-Blind Treatment					Follow-Up	
	Day 1 Visit	After Day 1, up to Week 24 Visits every 4 weeks (± 5 days)	Week 24 Visit (± 5 days)	After Week 24, up to Week 48 Visits every 8 weeks (± 5 days)	Week 48 Visit (± 5 days)/ Early Termination (ET)		
Plasma for disease, target and drug effect biomarkers	X	X Samples only to be collected at Week 4, Week 8, and Week 12	X		X	X	See Section 8.5.4 and Table 8 in Section 8.5.4. Participants should fast for at least 8 hours prior to the sample collection
Trough pharmacokinetic (PK) sampling	X	X	X	X	X	X	Trough (predose) samples will be collected at each visit. See Section 8.5.5

Procedure/Assessment	Double-Blind Treatment					Follow-Up
	Day 1 Visit	After Day 1, up to Week 24 Visits every 4 weeks (± 5 days)	Week 24 Visit (± 5 days)	After Week 24, up to Week 48 Visits every 8 weeks (± 5 days)	Week 48 Visit (± 5 days)/ Early Termination (ET)	
Study Medication						
Study medication administration training	X					Training maybe repeated as necessary at any study visit at the discretion of the investigator to maintain treatment compliance. See Section 8.4
Dispense study medication	X	X	X	X		See Section 8.4
Study medication return/reconcile		X	X	X	X	See Section 8.4

Table 3 Long-Term Bone Mineral Density and Immunogenicity Follow-Up Period Activities – Study MB130-069

Procedure/Assessment	6 Months After Week 52/PTFU (± 14 days) ^a	9 Months After Week 52/PTFU (± 14 days) ^b	12 Months After Week 52/PTFU (± 14 days) ^b	14 Months After Week 52/PTFU (± 14 days) ^b	Notes: 1 month is defined as 4 calendar weeks.
Concomitant medications since last visit	X				Selected medications that could impact bone mineral density assessment and nonalcoholic steatohepatitis (NASH) therapies taken after the end of study treatment (Section 8.4.8)
Dual-energy X-ray absorptiometry (DXA)	X				See Section 8.5.3.8. For participants who prematurely discontinue study medication, the follow-up DXA scan is not required unless the participant has completed at least Week 16
Anti-drug and anti-FGF21 antibodies	X	X	X	X	See Section 8.5.3.6 and Appendix 11
Blood chemistry				X	See Section 8.5.3.6
Hemoglobin A1c				X	See Section 8.5.3.6
Serum for disease, target and drug effect biomarkers	X				See Section 8.5.4 and Table 8. Participants should fast for at least 8 hours prior to the sample collection
Plasma for disease, target and drug effect biomarkers	X				See Section 8.5.4 and Table 8. Participants should fast for at least 8 hours prior to the sample collection

^a Month 6 samples will be collected from all participants.

^b Performed only in participants for whom Long-Term Immunogenicity Follow-Up Visits are required.

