6.3.3 Safety Monitoring

Safety monitoring will be in place during the entire study allowing early detection of any safety signals. Participants will undergo safety evaluations at each clinic visit and the investigator will conduct a thorough safety evaluation before dosing. Safety assessments will be regularly performed and will include assessments for AEs, focused symptom-directed physical examinations, and laboratory measurements.

Study results will be monitored by an independent DMC. The scope of responsibility for the DMC will be comprised of safety monitoring by masked treatment group however, the DMC may request treatment codes and/or efficacy summaries if indicated for safety/benefit assessment (see [Appendix 1](#)).

In addition to the DMC, the sponsor (blinded to treatment assignment) will monitor safety. All reported AEs will be assessed, including events of special interest for BMS-986036 (see Section [8.5.3.7](#)). The sponsor has developed a list of events of special interest for the BMS-986036 program based on the known biologic class effects, the mechanism of action, and data from unblinded clinical studies. These will include injection site reactions, gastrointestinal events, and bone-related events. Additionally, BMD and immunogenicity (anti-BMS-986036 and anti-FGF21 antibodies) will be monitored (see Section [8.5.3.6](#) and Section [8.5.3.8](#)). AEs on or around the time of development of anti-BMS-986036 and/or anti-FGF21 antibodies will be carefully evaluated.

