7.3 Safety Objective

To demonstrate the safety of BMS-986036 in adults with NASH and compensated cirrhosis throughout the course of the study, including BMD and immunogenicity.

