Participants will be stratified at randomization by country (Non-Japan/Japan). Participants in countries other than Japan will be stratified at randomization according to T2DM status (yes/no). Japanese participants will not be further stratified.

Randomized participants will receive their assigned double-blind study medication for a total of 48 weekly doses. The treatment will be administered by SC injection of 2 pre-filled syringes of study medication in the abdomen according to their assigned treatment arm (see Section 8.4.2). During the Double-Blind Treatment Period (Table 2 in Section 1), participants will be evaluated for safety and efficacy every 4 weeks (\pm 5 days) through Week 24 and every 8 weeks (\pm 5 days) after Week 24 through Week 48.

Participants will then return at Week 52 (\pm 5 days) for a PTFU Visit. Participants who discontinue study medication earlier than Week 48 will have an Early Termination (ET) Visit at the time of study medication discontinuation and will return for a PTFU Visit 4 weeks (\pm 5 days) after the ET Visit.

Participants will return 6 months (\pm 14 days) (1 month is defined as 4 calendar weeks) after the Week 52/PTFU Visit for DXA to assess BMD and for collection of samples for potential immunogenicity testing as well as serum and plasma biomarker samples (see Table 3 in Section 1). Participants at the Week 52/PTFU Visit may need to return at 9 months, 12 months, and 14 months (\pm 14 days) (1 month is defined as 4 calendar weeks) after the Week 52/PTFU Visit if required for immunogenicity testing, as described in Section 8.5.3.6 (see Table 3 in Section 1).

[figure not shown]
Figure 1 Study Design Schematic – Screening to Week 52/PTFU

ET = early termination; PTFU = Post-Treatment Follow-Up; QW = once weekly

^a For participants who discontinue study medication prematurely, liver biopsy will be performed at ET if the participant has completed at least Week 20. If a participant discontinues study participation prior to Week 20 they should consider having a liver biopsy at ET.

Figure 2 Study Schematic – Bone Mineral Density and Immunogenicity Follow-Up Visits After the Week 52/PTFU Visit (visit windows \pm 14 days) (1 month is defined as 4 calendar weeks)

DXA = dual-energy X-ray absorptiometry PTFU = Post-Treatment Follow-Up; QW = once weekly

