8.5.3.1 Adverse Events

The definitions of an AE or SAE can be found in [Appendix 9](#).

AEs will be reported by the participant (or, when appropriate, by a caregiver, surrogate, or the participant's legally authorized representative).

The investigator and any designees are responsible for detecting, documenting, and reporting events that meet the definition of an AE or SAE and remain responsible for following up AEs that are serious, considered related to the study medication or the study, or that caused the participant to discontinue before completing the study.

For weight change (increase or decrease) to be considered an AE, the change should be 10% or more from Baseline that cannot be explained by lifestyle modifications alone.

Contacts for SAE reporting are specified in Appendix 9.

Time Period and Frequency for Collecting AE and SAE Information

Sections 5.6.1 and 5.6.2 in the IB represent the Reference Safety Information to determine expectedness of SAEs for expedited reporting.

The collection of nonserious AEs should begin at initiation of study medication and continue until the Week 52/PTFU Visit (Section 1)..

Following the participant's written consent to participate in the study, all SAEs, whether related or not related to study medication, must be collected, including those considered by the investigator to be related to study medication or protocol-specified procedures. All SAEs will be collected through the Week 52/PTFU Visit and will be reported as described in Appendix 9.

The investigator must report any SAE occurring after the Week 52/PTFU Visit that is believed to be related to study medication or a protocol-specified procedure.

- Medical occurrences that begin before the start of study medication but after obtaining informed consent will be recorded on the appropriate Section of the eCRF

- All SAEs will be recorded and reported to sponsor or designee within 24 hours, as indicated in [Appendix 9](#)
- The investigator will submit any updated SAE data to the sponsor or designee within 24 hours of this information being available

Investigators are not obligated to actively seek AEs or SAEs in former study participants. However, if the investigator learns of any SAE, including a death, at any time after a participant has been discharged from the study, and he/she considers the event reasonably related to the study medication or study participation, the investigator must promptly notify the sponsor.

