Any significant worsening noted during interim or final physical exams, ECGs, or any other potential safety assessments required or not required by protocol should also be recorded as a nonserious AE or a serious AE, as appropriate, and reported accordingly. ECGs will be read and interpreted at the site or by a local reader.

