Participants with positive anti-drug and/or anti-FGF21 antibodies at the Week 52/PTFU Visit and without evidence of 2 consecutive stable or decreasing antibody titers will be followed for up to 14 months after the Week 52/PTFU Visit (1 month is defined as 4 calendar weeks) until antibody titers decrease for 2 consecutive visits (these additional visits will be conducted at approximately 9 months and 12 months after the Week 52/PTFU Visit). The sponsor or designee will inform the clinical site if a participant needs to return for

immunogenicity follow-up beyond 6 months. If, at 12 months after the Week 52/PTFU Visit, a participant has an increasing titer (compared to the previous titer), an additional follow-up visit will be performed at approximately 14 months (1 month is defined as 4 calendar weeks) after the Week 52/PTFU Visit; at this visit, anti-drug and anti-FGF21 antibodies, as well as additional laboratory assessments (basic metabolic panel, hemoglobin A1c [REDACTED], [REDACTED]), will be collected.

Participants who discontinue from the study prior to the Week 48 Visit will be offered additional Long-Term Immunogenicity Follow-Up Visits, as above. For these participants, prior immunogenicity results will be used to determine whether the participant should be offered Long-Term Immunogenicity Follow-Up Visits beyond the 6-month posttreatment assessment. Additional Long-Term Immunogenicity Follow-Up Visits should occur approximately 9, 12, and 14 months, if applicable (1 month is defined as 4 calendar weeks) after their last study visit.

Refer to the decision tree in [Appendix 11](#) for more details regarding Long-Term Immunogenicity Follow-Up Visits.

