8.5.3.7 Adverse Events of Special Interest

The sponsor has developed a list of AEs of Special Interest for the BMS-986036 program based on the known biologic class effects, the mechanism of action, and clinical study data. These will include the following:

- Injection site reactions
- Gastrointestinal events
 - Diarrhea, frequent bowel movements, nausea, vomiting, abdominal pain
- Bone-related events
 - Osteoporosis, osteopenia, bone and joint injuries, fractures (except tooth fracture), endocrine abnormalities of gonadal function not elsewhere classified (NEC), hyperparathyroid disorders, hypoparathyroid disorders, parathyroid disorders NEC, parathyroid analyses, metabolic bone disorders, vitamin D abnormal, vitamin D decreased, vitamin D deficiency, and miscellaneous events related to bone density

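### No adverse-event collection is scheduled after Week 52/PTFU, so nonserious or unrelated bone events are not systematically captured in the 24 weeks before the 6-month bone-safety DXA

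*Protocol*

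**What the plan says.** - **Schedule.** Table 2 has an adverse-event row that is marked at every visit through Week 52/PTFU. Table 3 has none at 6, 9, 12 or 14 months. At 6 months it schedules DXA, antibodies, biomarker samples and "Selected medications that could impact bone mineral density assessment and nonalcoholic steatohepatitis (NASH) therapies taken after the end of study treatment". Section 8.4.8 confirms that these drugs go on the eCRF.
- **Cut-off.** Under Protocol 8.5.3.1, nonserious AE collection "should begin at initiation of study medication and continue until the Week 52/PTFU Visit". Collection of all SAEs ends at the same visit. Later SAEs must be reported only if believed related to study medication or a protocol-specified procedure.
- **Undated clause.** Under Other Safety Considerations in the same section, significant worsening on physical examinations, ECGs or "any other potential safety assessments required or not required by protocol should also be recorded as a nonserious AE" or as a serious AE. No time limit is given.
- **Bone events.** Section 8.5.3.7 lists "Osteoporosis, osteopenia, bone and joint injuries, fractures (except tooth fracture" and further bone-related terms as AEs of special interest (AESIs).
- **Objective.** Section 7.3 sets the safety objective "throughout the course of the study, including BMD and immunogenicity". Under Section 8.2, participation runs through the Table 3 visits.
- **Analysis.** SAP 6.2.1 tabulates only treatment-emergent AEs, and SAP 8.4 closes that window 30 days after the last dose. SAP 7.2 reports data after Week 52/PTFU in a separate analysis.

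**The concern.** The sponsor kept bone follow-up open for about six months after treatment because bone effects are a named risk. For that period the plan collects the density measurement and the drugs that affect it, but it does not ask about the clinical events that both bear on. A bone-active drug could appear in the follow-up medication table (SAP 6.5.6.2) without the fracture or diagnosis that prompted it.

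For serious events, capture depends on a causality opinion given by a blinded investigator. The long-term report could then show few or no fractures by arm, and a reader could not tell whether none occurred or none were asked about.

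A worsened 6-month DXA also meets two instructions. The undated clause says to record it, while the cut-off says that nonserious collection has ended. Sites may resolve this differently.

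**Working it through.** **1. What is captured, side by side**

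| Item | Through Week 52/PTFU | Week 52/PTFU to 6-month visit |
|---|---|---|
| New nonserious AE | Collected | No required collection |
| SAE judged unrelated | Collected | No required collection |
| SAE believed related | Collected | Must be reported (8.5.3.1) |
| AESI already reported | Followed | Followed to resolution or stabilization (8.5.3.1) |
| Bone density | DXA at Screening and Week 48/ET | DXA at 6 months (8.5.3.8) |
| Bone-active drugs | Recorded | Recorded (Table 3, 8.4.8) |
| Worsening on a safety assessment | AE | Undated clause and cut-off conflict |

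The gap is the first two rows of the right-hand column, plus the conflict in the last row.

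**2. Length of the gap.** Section 8.1 fixes the return visit at 6 months ("1 month is defined as 4 calendar weeks) after the Week 52/PTFU Visit for DXA to assess BMD"). So 6 × 4 = 24 weeks, and the ± 14-day window gives 22 to 26. From Day 1 to the final DXA a completer contributes 52 + 24 = 76 weeks, so the share without scheduled AE collection is 24/76 = 31.6%.

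**3. Participant-time.** With about 155 randomized (Protocol 9.1): 155 × 24/52 = 71.5 participant-years if all attend. At 22 and 26 weeks it is 65.6 and 77.5.

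**4. Events at stake.** The documents give no rate of bone events, so the rates below are assumptions. Expected events E = 71.5 × rate; the chance of at least one is 1 − exp(−E).

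| Assumed rate per year | E, all arms | Chance of at least one |
|---|---|---|
| 0.5% | 0.36 | 30% |
| 1% | 0.72 | 51% |
| 2% | 1.43 | 76% |
| 3% | 2.15 | 88% |
| 5% | 3.58 | 97% |
| 6% | 4.29 | 99% |

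In one arm of 38 at 2% per year, E = 38 × 0.02 × 24/52 = 0.35. These figures count all bone events at the assumed rate, including related SAEs that would still be reported. They are therefore upper figures for what is missed at each rate.

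**5. Whether a recorded event would be tabulated.** For a participant dosed on schedule, dose 48 falls on Day 1 + 47 × 7 = Day 330. The SAP window closes on Day 330 + 30 = Day 360. Week 52 is Day 1 + 52 × 7 = Day 365, and the 6-month visit is Day 1 + 76 × 7 = Day 533. An event that first arises in follow-up is then outside the treatment-emergent window. Under SAP 6.2.1 it would be listed but not tabulated. Protocol 9.5.3 defines treatment-emergent with no upper limit, so the two documents also differ here.

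**The case against.** The case for leaving the plan alone has real content.

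- **Bone events are not simply lost.** Related SAEs remain reportable, AESIs already reported are followed, and the undated clause may catch a worsened DXA. Section 8.3.7 asks sites to consult the medical monitor if drugs affecting bone density are to be added in the first 6 months after Week 52/PTFU. This all stands, and it rules out saying that bone events go unrecorded. None of it asks every attending participant about fractures.
- **Low bone density can be counted anyway.** The DXA is centrally read, and SAP 6.2.5 analyses BMD with T- and Z-scores by visit, arm and pooled drug. This stands. A reader might infer that the long-term report can say nothing about osteoporosis, but the documents do not support that. What remains is fractures and clinical diagnoses.
- **The cut-off is a stated design.** Section 9.4.2 gives each safety endpoint its own timing. With a half-life of about 20 to 24 hours (Section 6.1.2), closing general AE collection about 5 weeks after the last dose is defensible. The statement in Section 6.3.3 that "Participants will undergo safety evaluations at each clinic visit" goes on to mention evaluation before dosing, so it can be read as describing dosing visits. This stands for AEs in general. It is weaker for bone, where the plan itself chose to keep looking off drug.
- **Antibody follow-up.** Participants with positive antibodies and no settled titres "will be followed for up to 14 months after the Week 52/PTFU Visit (1 month is defined as 4 calendar weeks", which is 14 × 4 = 56 weeks. A reader might infer that AEs should be collected and tabulated by arm at those visits too. The documents do not support this: visits at 9 to 14 months are held only for participants selected on titre, who would be almost all from active arms. Ascertainment would be unequal between arms, with essentially no placebo comparator.
- **Few events.** Counts this small cannot support comparison between arms. True, but the point concerns ascertainment of a named risk and does not rest on power.

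**Conclusion.** The point holds in a limited form. After Week 52/PTFU, new fractures and clinically diagnosed bone events that are nonserious or judged unrelated are not systematically captured during the 24 weeks before the 6-month DXA. The two instructions in Section 8.5.3.1 conflict for a worsened DXA and must be reconciled.

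The 24 weeks and the missing row come directly from the documents. The 71.5 participant-years assumes that all 155 attend. The 0.4 to 4.3 events rests on assumed rates of 0.5% to 6% per year and could be lower still. Nor does every participant have the follow-up DXA: Table 3 and Section 8.5.3.8 exempt those who stop medication before completing Week 16, while Section 8.1 says all participants, and these texts also need reconciling. No power or sample-size figure is affected. This is a cheap improvement to safety ascertainment and does not threaten the trial's main conclusions.

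**What to change.** 1. **Table 3:** add a row, *Bone-related AESIs (Section 8.5.3.7) since last visit*, at the 6-month visit for all participants who attend.
2. **Protocol 8.5.3.1:** extend collection of bone-related AESIs, related or not, to that visit, and reconcile this with the undated clause so that sites have one instruction for a worsened 6-month DXA.
3. **SAP 7.2:** tabulate these events by arm and for pooled BMS-986036, separately from treatment-emergent AEs.
4. **Leave the 9-, 12- and 14-month visits as they are.** Do not add an AE row or a by-arm AE table for them.

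The cost is one eCRF question at a visit already held, a short amendment and one table, with no new visit, scan or sample. The downside is slight site burden and the counting of some off-drug events unrelated to treatment.
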